4.6 Prior and Concomitant Therapies

Medications considered necessary for the patient's welfare may be given at the discretion of the investigator. The administration of all medication (including study product) must be recorded in the source document and the appropriate sections of the eCRF. During treatment with deferiprone, patients must not receive any other investigational product or any drugs that are known to cause neutropenia or agranulocytosis. A list of prohibited drugs is provided in [Appendix 2](#).

4.7 Rescue Medication

Rescue medication is defined as a newly prescribed medication or a change in dosage of a currently prescribed medication that has the potential to have an effect on dystonia symptoms and is provided because of a worsening of the patient's condition.

The use of rescue medication should be limited to circumstances judged as absolutely necessary by the investigator. Any use of a rescue medication must be documented, including

the reason. If a patient uses rescue medication for more than 2 events, the investigator should notify the sponsor to discuss the patient’s continued participation in the study.

Rescue medications for dystonia include, but are not limited to, the list of drugs provided in [Appendix 3](#).

5 STUDY PROCEDURES

The procedures and assessments to be conducted at each study visit are summarized in [Table 5.1](#) and are detailed in the section that follows.

Table 5.1 Table of study procedures

Procedure	Visit 1 ¹	Weekly Blood Draws	Telephone Contact	Visit 2	Visit 3	Visit 4 or Early Termination
Week:	0	1 to 78	1 and 2	26	52	78
Informed consent/assent	X					
Confirmation of eligibility	X					
Review of medical history	X					X
Serum pregnancy testing ²	X			X	X	X
Physical examination	X			X	X	X
Vital signs (including weight and height) ³	X			X	X	X
12-lead ECG	X					X
Contraceptive counseling	X			X	X	X
Hematology	X	X		X	X	X
Blood chemistry	X			X	X	X
Urinalysis	X			X	X	X
BAD	X			X	X	X
PGI-I				X	X	X

Procedure	Visit 1 ¹	Weekly Blood Draws	Telephone Contact	Visit 2	Visit 3	Visit 4 or Early Termination
Week:	0	1 to 78	1 and 2	26	52	78
Dose calculation/verify and adjust dose level	X			X	X	
Dispense study medication	X			X	X	
Remind patient to adjust dosage ⁴			X			
Collect used and unused study medication				X	X	X
Prior and concomitant medications	Throughout the study					
Adverse events and serious adverse events	Throughout the study					

¹ Visit 1 is the final visit (Month 18) of study TIRCON2012V1. It serves as the screening visit for TIRCON2012V1-EXT for all patients, and as the baseline for those patients who received placebo in TIRCON2012V1 and will now be receiving deferiprone for the first time. (For patients who received deferiprone in TIRCON2012V1, the measures obtained at the baseline visit of the TIRCON2012V1 study will be used as the baseline measures for TIRCON2012V1-EXT as well.)

² Sexually active females of childbearing potential only (if applicable; in cases where the investigator determines there is no reasonable risk of pregnancy because of significant incapacity, pregnancy testing will not be performed).

³ Height will be measured only at Visits 1 and 4

⁴ All patients, including those who were on deferiprone initially, will receive 5 mg/kg deferiprone b.i.d. for the first week. If the medication is tolerated and there are no signs of toxicity, the dose will be increased at Week 1 to 10 mg/kg b.i.d., and will be increased again at Week 2 to 15 mg/kg b.i.d. for the remainder of the study. Patients will receive a telephone call at these times to remind them to implement the increase in dosage, provided there are no safety concerns in doing so.

5.1 Visit Procedures

Visit 1 (Week 0)

This visit is the Month 18 visit of TIRCON2012V1: i.e., for patients who choose to continue on, the last visit of the initial study is considered the first of the extension study. For patients who had been on placebo and will now be receiving deferiprone for the first time, the data obtained at this visit will be treated as the baseline measures for TIRCON2012V1-EXT.

The following procedures will be done:

- Explain the extension study to the patient and/or authorized legal representative, and obtain written informed consent/assent
- Confirm eligibility criteria
- Review medical history
- Collect information about concomitant medications
- Ask patient about the use of any of the medications listed in [Appendix 3](#) or any other medication that has the potential to affect dystonia symptoms (e.g., spasticity, muscular rigidity, and parkinsonism), as follows:
 - If patient has been on a regular dosing regimen of any of these medications since the start of study TIRCON2012V1, verify that the regimen has been stable
 - If patient has been taking any of these medications on a PRN (as needed) basis since the start of study TIRCON2012V1, verify that treatment was interrupted prior to the current visit according to the following timelines:

Medication	Treatment interruption period prior to current visit
Baclofen	30 days
Trihexyphenidyl	30 days
Clonazepam	30 days
Tizanidine	30 days
Botox	60 days
Tetrabenazine	90 days

- If patient has a DBS system or Baclofen pump in place, verify that the DBS stimulation parameters or pump settings have been stable, as confirmed by the investigator

- Collect blood samples for the following assessments:
 - Hematology
 - Blood chemistry
 - Pregnancy testing for all sexually active females of childbearing potential (if applicable; in cases where the investigator determines there is no reasonable risk of pregnancy because of significant incapacity, pregnancy testing will not be performed)
- Collect a urine sample for urinalysis
- Measure vital signs, weight, and height
- Perform a 12-lead ECG
- Conduct contraceptive counseling for sexually active patients
- The following must be performed by a qualified investigator or a qualified delegate:
 - Conduct a physical examination
 - Record administration of the BAD in a standardized manner on videotape, and transmit tape to the evaluation center
- Verify dosage of study medication
- Dispense a 6-month supply of study medication
- Remind the patient/authorized legal representative to do the following:
 - Return all study medication containers at the next visit, whether empty or unused
 - Keep careful track of adverse events and medication(s) used
 - Interrupt therapy immediately in the event of fever (temperature ≥ 38.5 °C/101.3 °F), and promptly report any symptoms indicative of infection such as fever or flu-like symptoms
 - If patient is on a regular dosing regimen of any of the medications listed in [Appendix 3](#) or of any other medication that has the potential to affect dystonia symptoms, to stay on the same regimen for the duration of the study. Any change in dose and dosing regimen should be limited to circumstances judged as absolutely necessary by the investigator.
 - If patient is being treated with any such medications on a PRN basis, to use them only under circumstances judged as absolutely necessary by the investigator, and to interrupt treatment prior to the next study visit according to the following timelines:

Medication	Treatment interruption period prior to current visit
Baclofen	30 days
Trihexyphenidyl	30 days
Clonazepam	30 days
Tizanidine	30 days
Botox	60 days
Tetrabenazine	90 days

- If patient has a DBS system or Baclofen pump in place, to make every effort to maintain the same DBS stimulation parameters or Baclofen pump settings for the duration of the study. Any changes in settings should be limited to circumstances judged as absolutely necessary by the investigator.
- If leaving the study before completion, to return to the clinic for an Early Termination Visit as soon as possible and no later than 30 days following the last dose of study medication
- Provide patient with card containing contact information for emergency services, and advise that this card should be carried at all times
- Schedule next study visit

Weekly Blood Draws (every 7 ± 3 days)

Note: These blood draws can be conducted either at a local laboratory or at the study site.

- Collect blood sample for hematology assessment. The results are to be reviewed by the investigator in a timely manner when they are received from the laboratory.

Telephone Contact (Week 1 ±2 days and Week 2 ±2 days)

A study staff member will contact the patient and/or legal representative by telephone at Week 1 and Week 2 with the following queries and reminders, and will document the responses:

- Ask if treatment is proceeding satisfactorily. If the patient appears to be having difficulty, the telephone calls should be repeated as frequently as necessary.
- Remind the patient to increase the dosage of study medication at Week 1 from 5 mg/kg to 10 mg/kg, and at Week 2 from 10 mg/kg to 15 mg/kg, provided there are no safety concerns in doing so

- Remind the patient that if treatment is stopped early, to return to the clinic for an Early Termination Visit as soon as possible and no later than 1 month following treatment discontinuation
- Remind patient to interrupt therapy immediately in the event of fever (temperature ≥ 38.5 °C/101.3 °F), and to promptly report any symptoms indicative of infection such as fever or flu-like symptoms
- Ask if the patient has experienced any AEs or SAEs or has taken any concomitant medications. If yes, document these as specified in [Sections 7.2.1.2, 7.2.1.6, and 7.2.3.4](#).
- Reconfirm the next study visit
- Document the date and time of the contact; the person contacted (patient, parent, legal representative); and the name and signature of the staff member who conducted the call

Visit 2 (Week 26 \pm 14 days) and Visit 3 (Week 52 \pm 14 days)

The following procedures will be done:

- Collect information about concomitant medications
- Query patient about the use of any of the medications listed in [Appendix 3](#) or any other medication that has the potential to affect dystonia symptoms, as follows:
 - If patient has been on a regular dosing regimen of any of these medications since the start of study TIRCON2012V1, verify that the regimen has been stable
 - If patient has been taking any of these medications on a PRN basis since the start of study TIRCON2012V1, verify that treatment was interrupted prior to the current visit according to the following timelines:

Medication	Treatment interruption period prior to current visit
Baclofen	30 days
Trihexyphenidyl	30 days
Clonazepam	30 days
Tizanidine	30 days
Botox	60 days
Tetrabenazine	90 days

- If patient has a DBS system or Baclofen pump in place, verify that the DBS stimulation parameters or pump settings have been stable, as confirmed by the investigator

- Collect blood samples for the following assessments:
 - Hematology
 - Blood chemistry
 - Pregnancy testing for all sexually active females of childbearing potential (if applicable; in cases where the investigator determines there is no reasonable risk of pregnancy because of significant incapacity, pregnancy testing will not be performed)
- Collect a urine sample for urinalysis
- Measure vital signs and weight
- Conduct contraceptive counseling for sexually active patients
- The following must be performed by a qualified investigator or a qualified delegate:
 - Conduct a physical examination
 - Record administration of the BAD in a standardized manner on videotape, and transmit tape to the evaluation center
 - Administer the Patient Global Impression of Improvement
- Verify dosage of study medication
- Dispense a 6-month supply of study medication
- Collect any empty containers or unused medication from the previous 6 months, and perform drug accountability
- Remind the patient/authorized legal representative to do the following:
 - Return all study medication containers at the next visit, whether empty or unused
 - Keep careful track of adverse events and medication used
 - Interrupt therapy immediately if an infection develops, and immediately report any symptoms indicative of infection such as fever, or flu-like symptoms
 - If patient is on a regular dosing regimen of any of the medications listed in [Appendix 3](#) or of any other medication that has the potential to affect dystonia symptoms, to stay on the same regimen for the duration of the study. Any change in dose and dosing regimen should be limited to circumstances judged as absolutely necessary by the investigator.
 - If patient is being treated with any such medication on a PRN basis, to use them only under circumstances judged as absolutely necessary by the investigator, and to interrupt treatment prior to the next study visit according to the following timelines:

Medication	Treatment interruption period prior to next visit
Baclofen	30 days
Trihexyphenidyl	30 days
Clonazepam	30 days
Tizanidine	30 days
Botox	60 days
Tetrabenazine	90 days

- If patient has a DBS system or Baclofen pump in place, to make every effort to maintain the same DBS stimulation parameters or Baclofen pump settings for the duration of the study. Any changes in settings should be limited to circumstances judged as absolutely necessary by the investigator.
- If patient decides to leave the study before completion, return to the clinic for an Early Termination Visit as soon as possible and no later than 1 month following the last dose of study medication
- Schedule next study visit

Due to the difficulties that travel may pose for patients with PKAN, participants will have the option of arranging for the Visit 2 and Visit 3 assessments to be done locally instead, as follows:

- *At patient's home, via telephone:* Collection of information on concomitant medications, use of medications with potential to affect dystonia symptoms, and stability of DBS stimulation parameters or pump settings; conducting of contraceptive counseling; administration of the PGI-I; verification of dosage of study medication; reminders to patient as detailed above
- *At a local doctor's office:* Physical examination; measurement of weight; measurement of vital signs.
- *At a local laboratory:* Blood and urine samples for safety tests; blood sample for pregnancy test if applicable.
- *At patient's home, via videoconferencing:* Video recording for BAD assessment. Patients and their family members who will not be travelling to the site for Visits 2 and 3 will be provided with recording equipment and trained in how to operate it. On the day of the assessment, the study doctor will connect to the patient's home via videoconferencing, and will direct the patient what to do while the family member (or other appropriate individual) records it. Instructions will be provided on how to upload the video for transmission to the site and to the central assessors.

- *Via courier:* From patient to site: Return of used and unused study medication containers from the past 6 months. From site to patient: Provision of study medication for the next 6 months.

Visit 4 (Week 78 ± 14 days) / Early Termination Visit

The following procedures will be done:

- Review medical history
- Collect information about concomitant medications
- Query patient about the use of any of the medications listed in [Appendix 3](#) or any other medication that has the potential to affect dystonia symptoms, as follows:
 - If patient has been on a regular dosing regimen of any of these medications since the start of study TIRCON2012V1, verify that the regimen has been stable
 - If patient has been taking any of these medications on a PRN basis since the start of study TIRCON2012V1, verify that treatment was interrupted prior to the current visit according to the following timelines:

Medication	Treatment interruption period prior to current visit
Baclofen	30 days
Trihexyphenidyl	30 days
Clonazepam	30 days
Tizanidine	30 days
Botox	60 days
Tetrabenazine	90 days

- Collect blood samples for the following assessments:
 - Hematology
 - Blood chemistry
 - Pregnancy testing for all sexually active females of childbearing potential (if applicable; in cases where the investigator determines there is no reasonable risk of pregnancy because of significant incapacity, pregnancy testing will not be performed)
- Collect a urine sample for urinalysis
- Measure vital signs, weight, and height
- Perform a 12-lead ECG

- Conduct contraceptive counseling for sexually active patients
- The following must be performed by a qualified investigator or a qualified delegate:
 - Conduct a physical examination
 - Record administration of the BAD in a standardized manner on videotape, and transmit tape to the evaluation center
 - Administer the Patient Global Impression of Improvement
- Collect any empty containers or unused medication from the previous 6 months, and perform drug accountability
- Instruct the patient/authorized legal representative to report any AEs that occur in the next 14 days and any SAEs that occur in the next 30 days

Any ongoing AE or SAE is to be followed until one of the following outcomes:

- AE/SAE is resolved
- Patient's condition stabilizes
- AE/SAE is otherwise explained
- Patient is lost to follow-up

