4.5.3 Treatment Interruptions

As in the initial study, patients will be provided with a card containing contact information for emergency services which they are to carry at all times, and will be advised to promptly report any symptoms indicative of infection such as fever or flu-like symptoms. Treatment will be interrupted under the following circumstances:

- If a patient develops an infection, therapy will be interrupted based on the investigator's judgment. If ANC $<1.5 \times 10^9/L$., neutrophil count must be obtained and monitored more frequently.
- If a patient develops a fever (defined as ≥ 38.5 °C or 101.3 °F), therapy must be interrupted immediately, and a CBC and differential count must be obtained.

Therapy with study medication can be re-initiated once all symptoms have been resolved and it is deemed safe by the investigator. See [Section 7.2.1.8](#), Adverse Events of Special Interest.

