7.2.1.8 Adverse Events of Special Interest

An important AE that has a known association with deferiprone is **neutropenia**, defined as an absolute neutrophil count (ANC) less than $1.5 \times 10^9/L$. The severity of neutropenia is categorized as follows:

Mild neutropenia:	A confirmed ANC $\geq 1.0 \times 10^9/L$ and $< 1.5 \times 10^9/L$.
Moderate neutropenia:	A confirmed ANC $\geq 0.5 \times 10^9/L$ and $< 1.0 \times 10^9/L$.
Severe neutropenia/agranulocytosis:	A confirmed ANC $< 0.5 \times 10^9/L$.

“Confirmed” means that the ANC has been found to be within the specified range on 2 consecutive measurements a maximum of 3 days apart. If both consecutive counts are below $1.5 \times 10^9/L$ but are not within the same range, a third count is required to determine the severity category. Neutropenia is considered to be resolved when ANC is $\geq 1.5 \times 10^9/L$ on 2 consecutive counts.

Management of Neutropenia

Patients will be scheduled for weekly hematology testing throughout the study, and the results will be forwarded to the investigator. If an ANC $< 1.5 \times 10^9/L$ is detected, the patient and, if possible, the primary care physician, are to be promptly notified. In addition, since both fever and infection can be associated with neutropenia, patients will be instructed to do the following:

- In the event of a temperature ≥ 38.5 °C/101.3 °F, they are to immediately discontinue treatment and contact the investigator at the 24-hour number provided. The investigator will request that CBC and differential count be obtained.
- If they develop any symptoms of infection, they are to promptly report this to the investigator at the 24-hour number provided. The investigator will then determine whether or not treatment should be interrupted.

The management of neutropenia depends on its severity, as described below.

Mild neutropenia:

- Instruct patient to interrupt deferiprone immediately.
- Repeat the ANC count daily until resolution.
- If possible, arrange for patient to be seen by a physician the same day for a physical examination, assessment of AEs, and a review of concomitant medications/therapies. If this is not possible, contact patient by phone to obtain information on AEs and medications.
- Advise patient to enter protective isolation, if possible.
- Notify the sponsor of the event by submitting the SAE form.

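### The Visit 2 and Visit 3 patient reminder leaves out the rule to stop deferiprone at once at 38.5 °C or above, and makes any infection the trigger instead

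*Protocol*

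**What the plan says.** Protocol 4.5.3 (Treatment Interruptions) separates two situations. For a temperature of 38.5 °C (101.3 °F) or above, "therapy must be interrupted immediately, and a CBC and differential count must be obtained". For infection the rule is softer: "If a patient develops an infection, therapy will be interrupted based on the" investigator's judgement.

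Protocol 7.2.1.8 turns this into instructions for patients and gives the reason: "since both fever and infection can be associated with neutropenia". At 38.5 °C or above, "they are to immediately discontinue treatment and contact the investigator at the 24-hour number provided". For symptoms of infection the patient reports, and "The investigator will then determine whether or not treatment should be interrupted".

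In Protocol 5.1, the Visit 1 reminder and the Week 1 and Week 2 telephone calls repeat the fever rule with the 38.5 °C threshold. The reminder list shared by Visits 2 and 3 reads differently: "Interrupt therapy immediately if an infection develops, and immediately report any symptoms indicative of infection such as fever, or flu-like symptoms". Section 5.1 also has that list given by telephone to patients who have these two visits done locally.

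**The concern.** The Visit 2/3 bullet departs from the rest of the protocol in two ways.

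1. **The fever stop is missing.** This is the main point. Elsewhere a measured temperature is enough to stop the drug. Here the trigger is that an infection develops, and fever is only an example of a symptom to report. A patient who has a fever but does not think of it as an infection can follow this reminder exactly by calling in while still taking deferiprone.
2. **The infection stop is automatic.** The bullet gives the patient a decision that 4.5.3 and 7.2.1.8 give to the investigator. This is cautious wording, and no safety consequence is claimed for it.

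The first point matters because the fever rule exists for neutropenia. Protocol 1.3 names agranulocytosis as the most serious adverse event associated with deferiprone, seen in about 1.7% of patients in pooled trials, with some fatal post-marketing reports.

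**Working it through.** The plan gives no figure to reproduce. The check is a comparison of texts, followed by simple counts of reach.

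**Step 1. The rule wherever it appears in the protocol**

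| Place | Temperature of 38.5 °C or above | Infection or its symptoms |
|---|---|---|
| 4.5.3 | Stop immediately; CBC and differential | Investigator decides on interruption |
| 7.2.1.8 | Patient stops immediately and calls | Patient reports; investigator decides |
| 5.1, Visit 1 (Week 0) | Stop immediately | Report promptly |
| 5.1, calls (Weeks 1 and 2) | Stop immediately | Report promptly |
| 5.1, Visits 2 and 3 (Weeks 26 and 52) | No threshold, no stop; fever to be reported immediately | Stop immediately; report symptoms immediately |

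Four of the five places state the 38.5 °C stop. The Visit 2/3 list is the only one that does not, and the only one that has the patient stop for infection without the investigator's decision.

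**Step 2. Reminders affected**

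Reminders scheduled in 5.1 before the final visit fall at Weeks 0, 1, 2, 26 and 52. The stop is present at Weeks 0, 1 and 2 and absent at Weeks 26 and 52, so 2 of 5 lack it.

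**Step 3. Time over which the differing text is the latest scheduled reminder**

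From Week 26 to Week 78: 78 − 26 = 52 weeks, and 52/78 = 67% of the planned study (nominal visit weeks).

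**Step 4. Patients**

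SAP 3.2 gives 44 from the deferiprone group and 24 from the placebo group: 44 + 24 = 68. This is an upper bound, because the number still on treatment at Week 26 is not given.

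**Step 5. Do the weekly counts close the gap?**

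Protocol 5.1 sets blood draws every 7 ± 3 days, so scheduled counts may be 7 + 3 = 10 days apart by the stated window. They are a useful backstop but do not replace action on the day of a fever.

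**Step 6. Where the gap lies**

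Once the patient reports a fever of 38.5 °C or above, 4.5.3 requires interruption, a CBC and a differential count. The exposed interval therefore runs from the onset of fever to the call, which is when the patient acts on the reminder alone.

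**The case against.** The strongest reply is that this is an omission from a reminder and does not countermand the rule. Nothing in the bullet tells a febrile patient to carry on. Section 7.2.1.8 is a standing instruction tied to no visit, 4.5.3 makes the interruption mandatory, and patients have heard the threshold at three earlier contacts. The bullet also calls fever a sign of infection and says to stop for infection, so many patients would stop anyway, perhaps below 38.5 °C. Immediate reporting is required, and 4.5.3 adds another safeguard: "patients will be provided with a card containing contact information for emergency services which they are to carry at all times".

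All of this is fair, and it limits the consequence. It does not make the texts agree. Reading fever as infection is an inference left to the patient, where the rest of the protocol gives an objective threshold. The 52 of 78 weeks must not be read as time without the rule, since 4.5.3 and 7.2.1.8 apply throughout.

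A second objection is that restoring investigator judgement for infection removes a cautious stop, although 7.2.1.8 links infection as well as fever to neutropenia. That cost is real but small, and it is what 4.5.3 and 7.2.1.8 already intend. The cautious stop also does not leave the patient free to restart alone: "Therapy with study medication can be re-initiated once all symptoms have been resolved and it is deemed safe by the investigator".

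Finally, consent material is not in the documents reviewed, so what patients were given in writing cannot be judged.

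**Conclusion.** The concern holds, with high confidence, because it rests on direct comparison of the protocol's own text. The Visit 2/3 reminder omits the 38.5 °C stop stated in 4.5.3, 7.2.1.8, the Visit 1 reminder and the Week 1 and 2 calls. It also conflicts with 4.5.3 and 7.2.1.8 on who decides to interrupt for infection. Nothing suggests a deliberate change of rule.

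It should be corrected because it is a working safety instruction for the drug's most serious hazard. The counts above measure reach only: the documents give no rate of fever or infection and no number at risk at Week 26, so no excess risk can be calculated. The practical gap depends on a patient who relies on the later reminder and does not treat fever as infection. No endpoint, analysis population or statistical method is affected.

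**What to change.** Replace the Visit 2/3 bullet with one that says three things:

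- stop study drug at once if the temperature reaches 38.5 °C (101.3 °F) or more;
- report fever, flu-like symptoms or any other sign of infection immediately;
- for infection without fever, the investigator decides whether to interrupt.

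Use the same text for the telephone reminders when Visits 2 and 3 are done from home. Do not simply copy the Visit 1 bullet: it asks for prompt reporting, which is weaker than the immediate reporting already in the Visit 2/3 text.

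The cost is a one-bullet protocol clarification and an update to the reminder text that sites use. Urgency of reporting is unchanged. The one downside is slightly less automatic interruption for infection without fever, which is the position 4.5.3 already takes.
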